## **6.6. Pooling of Centers**

There are approximately 60 sites participating in Studies 1501 and 1502 from US, Canada, Belgium, Denmark, France, Germany, Italy, Japan, Norway, Spain, Sweden, United Kingdom, and Australia. For Study 1502 Japan was added in 2019 whereas Europe and Australia started in 2016. Approximately 36 sites will contribute randomized subjects to Study 2. It is likely that the number of patients recruited by some sites will be small. The primary analysis will use data pooled across sites. Differences among regions may be explored if warranted.

## **6.7. Subgroups**

Select efficacy and safety outputs may be further broken down by the following subgroups:

- Age strata: <6 years, ≥6 years.
- Japanese subjects, Non-Japanese subjects
- Sex
- Race
- SCN1A Mutation Yes/No

PUBLIC COPY

This document cannot be used to support any marketing authorization application and any extensions or variations thereof.

This document is confidential.

## 7. Demographic, Other Baseline Characteristics and Medication

### 7.1. Subject Disposition and Withdrawals

Subject disposition will be presented per treatment group and overall.

For describing the subject disposition, the following will be summarized by number and percentage:

- Subjects enrolled (only overall)
- Subjects enrolled but not randomized and reason for not-randomized (only overall)
- Subjects randomized
- SAF
- mITT
- PP
- Subjects assigned to SAF, mITT, PP and discontinued the study and reason.
- Number of subjects in the trial per trial period/phase (Titration Phase, Maintenance Phase, Follow-up Period) will be presented for SAF and mITT sets.
- Trial completers.
  - Trial completers continuing in the open-label extension study
  - Trial completers not continuing in the open-label extension study

For subjects enrolled but not randomized to treatment and for the reasons for not being randomized the denominator used to calculate the percentage will be the number of enrolled subjects. For all other calculations the denominator will be the number of subjects randomized.

All subject data will be listed using the enrolled population and sorted by treatment and site.

### 7.2. Demographic and Other Baseline Characteristics

Subject demographics and baseline characteristics will be summarized descriptively per treatment group and overall, for the SAF and mITT populations as well as for Japan and Non-Japan sub-groups.

The following demographic characteristics will be summarized:

- Age[Years]
- Categorical age as <6 years and ≥6 years.
- Sex
- Race
- Ethnicity
- Height [m]
- Weight [kg]
- BMI [kg/m^2]

All subject demographics data will be listed for the enrolled population.

Below are conversions that may be applied:

Age at Study day 1 = (Study day 1) visit date - date of birth + 1) / 365.25 and truncated to complete years.

Height (in cm) = height (in inches) \* 2.54

This document is confidential.

Weight (in kg) = weight (in lbs) \* 0.4536

BMI (kg/m^2) = Weight(kg)/[Height(m)]

### **7.3. Medical History and Concomitant Diseases**

Medical history will be summarized and sorted alphabetically, by primary System Organ Class and Preferred Term coded via the most recent version of Medical Dictionary for Regulatory Activities (MedDRA). The number and percentage of subjects will be displayed for each System Organ Class and Preferred Term within treatment group.

Medical history will be presented for the SAF population.

All prior and concomitant medical history data of subjects will be listed for the enrolled population.

### **7.4. Other Baseline Characteristics**

Other baseline characteristics such as epilepsy/seizure history and epilepsy genotype panel data will be descriptively summarized as per data type (categorical). Genetic data will be summarized as the proportion who have or do not have mutations of the SCN1A gene. Additional analyses of genetic data may be prepared in a separate report.

All subject baseline characteristics will be listed for the enrolled population.

### **7.5. Medication**

#### **7.5.1. Prior Medication and Concomitant Medication**

Medication (collected on prior medications, and concomitant medications eCRF page) will be coded using the World Health Organization Drug Dictionary (WHO-DD) Format B3 Version Sep2017 or later.

The following algorithm will be used to define prior and concomitant.

Prior medications will be those with a stop date prior to first dose administration.

Concomitant medications will be defined as those medications that were initiated after study drug administration or those medications that were ongoing at the date of first study drug administration.

The medication will be assumed to be prior medication if it cannot be definitively shown that the medication did not start or continue during the treatment period.

If the start date or stop date of a medication is partially missing, the date will be compared as far as possible with the date of the start of administration of study drug. The following approach will be taken:

- If the start date of medication is complete and occurs on or after the day of the first full dose, the medication will be assumed concomitant. If the start date occurs prior to the first full dose date but the end date is on or after the first dose date or the medication is recorded as ongoing, the medication will be considered concomitant.
- If the start day is missing but the start month and year are complete, a medication will only be excluded as being concomitant if the start month/year is before the month/year of study drug administration and if the stop date (either full date, month and year if missing day, or year if missing month and day) is before study drug administration.
- If the start day and month are missing but the start year is complete, a medication will only be excluded as concomitant if the start year is before the year of study drug administration and if the stop date (either full date, month and year if missing day, or year if missing month and day) is before study drug administration.

**This document is confidential.**

**Statistical Analysis Plan**

Sponsor: Zogenix International Limited; Protocol No.: ZX008 Study 2 (ZX008-1501 and ZX008-1502)

---

- If the start date is completely missing and the stop date is prior to first dose or completely missing, the medication will be assumed to be a prior medication.

Medication will be summarized and sorted alphabetically separately for prior and concomitant medication by Anatomical Therapeutic Chemical (ATC) categories (Level 2: pharmacological or therapeutic subgroup and Level 3: chemical or therapeutic or pharmacological subgroup) and WHO-DD drug code. For each medication the number and percentage of subjects will be displayed.

Medication summary tables will be presented for the SAF population.

All prior and concomitant medications/treatments will be listed for the enrolled population.

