**Adverse Events by Concomitant Medication Usage**

The following summary tabulations will be provided to explore the incidence of AEs by concomitant medication usage:

- Valproate
- Clobazam
- Topiramate

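### The medication date rules (Study 2 SAP 7.5.1, Study 1 SAP 6.2.5) class a drug with neither start nor stop date as prior, with no exception for a drug recorded as ongoing, against the same sections' definitions and partial-date rules

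*SAP*

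**What the plan says.** Study 2 SAP 7.5.1 first gives two definitions. Prior: "Prior medications will be those with a stop date prior to first dose administration". Concomitant: drugs begun after study drug administration, or "those medications that were ongoing at the date of first study drug administration". Study 1 SAP 6.2.5 has an equivalent definition of concomitant but no definition of prior.

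Both SAPs then set a default for cases where use in the treatment period is uncertain: "The medication will be assumed to be prior medication if it cannot be definitively shown that the medication did not start or continue".

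Four bullets follow, the same in substance in both SAPs:

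- Complete start date: a drug started before first dose is concomitant if it ended on or after first dose, "or the medication is recorded as ongoing, the medication will be considered concomitant".
- Start month and year known: the drug is excluded as concomitant only if both its start and its stop fall before study drug.
- Start year only: "a medication will only be excluded as concomitant if the start year is before the year of study drug administration" and the stop date also precedes study drug.
- No start date at all: the drug is classed as prior under the rule that begins "If the start date is completely missing and the stop date is prior to first dose or completely missing, the medication will be assumed".

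Study 2 SAP 7.5.2 and Study 1 SAP 6.2.6 handle antiepileptics in the same way. In Study 2 the concomitant class feeds the concomitant-medication table (14.1.4.2), the concomitant antiepileptic tables (14.1.4.4.1 and 14.1.4.4.2), adverse events by valproate, clobazam and topiramate use (14.3.1.13 to 14.3.1.15), and seizure frequency by valproate and clobazam use (14.2.15.6 and 14.2.15.7). Section 10.3 introduces the adverse-event set: "The following summary tabulations will be provided to explore the incidence of AEs by concomitant medication usage".

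**The concern.** A drug that is still being taken has no stop date. If its start was never recorded either, it meets the condition of the last bullet and is classed as prior. The clause on drugs recorded as ongoing stands only in the bullet for a complete start date and is not repeated for a missing one.

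The default sentence points the same way. When on-treatment use cannot be ruled out, it assumes that there was none. The Study 2 SAP takes the opposite line for adverse events in section 6.4: dates are imputed to the longest possible duration, and a missing ongoing flag means that the event is taken as still present.

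At stake is the description of background therapy in a trial of add-on treatment. A current antiepileptic with neither date can leave the concomitant tables. In Study 2 its user can then be counted among the non-users in the by-drug tables, which would blur any difference between users and non-users.

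**Working it through.** The SAPs state no figure for this rule, so the check is to apply it literally to each combination of dates and compare the result with the section's own definitions. Known or partial start dates are taken to lie before study drug. A partial start means month and year, or year only.

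| Start date | Stop date | Ongoing flag | Class by bullets or default | Class by definitions |
|---|---|---|---|---|
| Complete | Missing | Yes | Concomitant | Concomitant |
| Complete | Missing | Blank | No bullet applies; default gives prior | Undetermined |
| Partial | Missing | Yes | Concomitant | Concomitant |
| Partial | Missing | Blank | Concomitant | Undetermined |
| Missing | Before first dose | n/a | Prior | Prior |
| Missing | On or after first dose | n/a | No bullet applies | Concomitant |
| Missing | Missing | Yes | **Prior** | **Concomitant** |
| Missing | Missing | Blank | **Prior** | Undetermined |

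Three things follow.

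1. With both dates missing and the drug flagged ongoing, the last bullet and the definition of concomitant give opposite answers. The SAP does not say which prevails.
2. With both dates missing and no flag, the last bullet gives prior, although Study 2's definition of prior requires a stop date that the record does not have.
3. Compare the partial-start rows with the last two rows. A drug with only its start year and no stop date is concomitant; remove the year and it becomes prior. Less knowledge about the start reverses the class, and no reason is given.

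If the last bullet followed the partial-date bullets, only the last two rows would move among the records that the bullets cover. Reversing the default sentence would also move the row with a complete start, no stop date and no flag.

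**Scale, for illustration only.** Take 40 subjects per arm (Study 2 SAP 2.5) and assume that 60% use a given drug: 40 × 0.60 = 24 users and 16 non-users. Let *f* be the share of users whose record lacks both dates. Then 24*f* users move, and they make up 24*f* / (16 + 24*f*) of the tabulated non-users.

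| Assumed *f* | Users moved per arm | Users left of 24 | Share of non-user group |
|---|---|---|---|
| 1% | 0.24 | 23.76 | 0.24 / 16.24 = 1.5% |
| 5% | 1.2 | 22.8 | 1.2 / 17.2 = 7.0% |
| 10% | 2.4 | 21.6 | 2.4 / 18.4 = 13.0% |
| 20% | 4.8 | 19.2 | 4.8 / 20.8 = 23.1% |

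Neither the 60% nor any value of *f* comes from the documents, and *f* may be close to zero.

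**The case against.** The strongest reply is that the affected cell is narrow. The record must lack even a start year. A teenager on valproate since infancy is concomitant under the partial-date bullets as soon as an approximate year is entered, and nothing shows that records without a year are common. This stands: the text supports that such drugs can drop out, not that they do.

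Four stronger readings are tempting, and the documents do not support them.

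- A reader might infer that every ongoing drug with both dates missing is definitely misclassified. The definition of concomitant points the other way, so for flagged records the fault is a contradiction left to the programmer.
- A reader might infer that all errors run away from concomitant. The partial-date bullets lean the other way, since a missing stop date keeps the drug concomitant.
- A reader might infer that a prohibited serotonergic or enzyme-inhibiting drug would be hidden. All prior and concomitant drugs are listed, inappropriate concomitant intake is a deviation category (Study 2 SAP 5.5), and serotonin syndrome is defined by symptoms, with events of special interest found by standardised query or manual review (10.3). None of this uses the flag.
- A reader might infer harm to the efficacy conclusion. The models for the primary and key secondary endpoints contain no concomitant-drug term, the adverse-event tables by drug are exploratory and carry no p-values, and Study 1 plans no by-drug tables of this kind.

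It can also be said that a concomitant default would sweep in abandoned drugs with no dates, which are plausible in a treatment-resistant disease. That is fair and shapes the fix.

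**Conclusion.** The concern holds as an internal contradiction with a wrong default. In both SAPs a record with neither date is classed as prior even if flagged ongoing. This conflicts with the definition of concomitant, with Study 2's definition of prior, and with the partial-date bullets.

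Its reach is limited. It touches only records that lack both dates, in the concomitant-medication and antiepileptic tables of both studies and in the exploratory by-drug tables of Study 2. How often such records occur is not stated, so the illustrative percentages carry no weight in this conclusion. The contradiction rests on the wording alone. It should be corrected because the correction is cheap, not because it threatens the primary or key secondary results.

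**What to change.** In Study 2 SAP 7.5.1:

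1. State that any record flagged ongoing is concomitant, whatever its start date.
2. Class a drug as prior only when a stop date, even a partial one, shows that it ended before first dose.
3. In the last bullet, delete the words that extend it to a completely missing stop date, and reverse the default sentence so that unresolved cases are concomitant.
4. For records with no dates and no ongoing flag, use the CRF page of entry. Section 7.5 names separate prior and concomitant pages.

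Section 7.5.2 then inherits the change for antiepileptics. Make the same changes to Study 1 SAP 6.2.5, which carries over to 6.2.6. That SAP names a combined prior/concomitant page, so step 4 helps there only if the page itself separates the two. Study 1 was reported in September 2017 (Study 2 SAP 2.3), so the practical step for it is to state how such records were classed.

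The cost is a few sentences in each SAP and about a line of derivation code. The downside is that some truly prior drugs with no dates may be listed as concomitant; the page rule limits this.

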#### 7.5.2. Prior and Concomitant Antiepileptic Treatments

Antiepileptic treatments (collected on the prior antiepileptic medications, and concomitant medications eCRF page) will be coded using the World Health Organization Drug Dictionary (WHO-DD) Format B3 Version Sep2017 or later. Anti-epileptic medications will be identified using any drug entered on the prior-antiepileptic medication.

Prior and concomitant antiepileptic medications will be defined and analyzed for the safety population similar to concomitant medications as described in Section 7.5.1.

All prior and concomitant antiepileptic treatments will be listed for the enrolled population.

This document is confidential.

## 8. Efficacy

The analysis of the primary and secondary efficacy parameters will be performed on the mITT population, except where noted.

The primary and key secondary efficacy analyses will be repeated on the PP Population.

All primary and key secondary variables will be analyzed for data obtained for the T+M period, and will be repeated for data obtained during the M period only.

### 8.1. Primary Efficacy Endpoint and Analysis

The primary efficacy endpoint is the change in the mean convulsive seizure frequency (MCSF) per 28 days between the Baseline and T+M periods. For each subject, the CSF will be calculated from all available data collected during the Baseline and T+M Periods, and the treatment group mean convulsive seizure frequency per 28 days (MCSF) will be calculated for the baseline and T+M period.

The baseline period is the 42 days immediately preceding the Randomization visit and the T+M period is planned for 14 weeks. However, actual durations will be computed for each subject based on the individual subject's start and stop dates for each period, except that if the baseline period is longer than 42 days, the average for the baseline period will be taken over the 42 days immediately preceding the Randomization visit.

The convulsive seizure frequency will be counted from the daily diary records provided by the Subject or Parent/Caregiver.

For any individual subject, the convulsive seizure frequency per 28 days during the baseline period ( $CSF_B$ ) will be derived as follows:

$$CSF_B = \frac{28 \times \text{Total number of convulsive seizures during the Baseline Period}}{\text{Total number of days in the Baseline Period with nonmissing diary data}}$$

For each treatment group, the mean is obtained by averaging over the subjects in the treatment group.

Similarly, for each subject, the convulsive seizure frequency per 28 days for the T+M period ( $MCSF_{T+M}$ ) is derived as below:

$$CSF_{T+M} = \frac{28 \times \text{Total number of convulsive seizures in the T + M period}}{\text{Total number of days in the T + M period with nonmissing diary data}}$$

The percentage change from baseline for any individual subject will be estimated by

$$(CSF_{T+M} - CSF_B) * 100 / CSF_B$$

The difference from baseline will be estimated by  $CSF_{T+M} - CSF_B$ .

Corresponding treatment group means are designated with "M" preceding the quantity. For each treatment group, descriptive statistics for MCSF during baseline, T+M and M only, as well as the differences and % changes from baseline, will include the number of observations, mean, standard deviation, median, minimum and maximum, overall and by age group (<6 years, ≥6 years).

This document is confidential.

## Primary Analysis

### T+M Period:

The primary analysis will compare the ZX008 0.8 mg/kg/day group to the placebo group using a two-sided test at the  $\alpha=0.05$  level of significance.

The primary endpoint ( $CSF_{T+M}$ ) will be analyzed using an analysis of covariance (ANCOVA) model with treatment group (three levels) and age group (< 6 years,  $\geq 6$  years) as factors, log baseline  $CSF_B$  as a covariate and log  $CSF_{T+M}$  as response. Treatment group mean differences from placebo will be estimated via least squares means from the analysis model along with 95% confidence intervals and associated 2-sided p-values. Estimated treatment differences and CI endpoints will be exponentiated for presentation.

The null hypothesis

$$H_0: \mu_{Z0.8} - \mu_P = 0,$$

will be tested against the alternative

$$H_A: \mu_{Z0.8} - \mu_P \neq 0,$$

where  $\mu_{Z0.8}$  and  $\mu_P$  represent the ZX008 0.8 mg/kg and Placebo group means (on the log scale), respectively.

Rejection of the null hypothesis in favor of the alternative, in the presence of a statistically significantly smaller mean convulsive seizure frequency for the treatment group compared to the placebo group, (two-sided p-value < 0.05) will be regarded as evidence of a treatment benefit in favor of the 0.8 mg/kg group.

Sample SAS code for the ANCOVA described above is as follows:

```
proc glm data=temp;
  class agegrp trtp;
  model csftm = bcsf agegrp trtp / SS3;
  lsmeans trtp / pdiff stderr;
```

where trtp = randomized treatment group (with codes 1, 2, 3 indicating placebo, 0.2 mg, and 0.8 mg groups).

```
bcsf = log( CSFB ),
csftm = log( CSFT+M + 1 ),
agegrp = age group.
```

Additional statements may be used to obtain estimates and associated 95% confidence intervals. Endpoints of the CIs may be exponentiated to obtain CI on the original scale. Fitted values and residuals will be plotted to check model assumptions.

Since the ANCOVA used in the primary analysis relies on assumptions of normality, the primary endpoint will also be analyzed using a nonparametric method that does not require as stringent assumptions. A nonparametric ANCOVA will be used to analyze the data, with ranks of the baseline  $CSF_B$  as a covariate and ranks of  $CSF_{T+M}$  as response, and the results will be used to assess the primary objective. If normality assumptions are not met, the results of the nonparametric test will be used to assess the primary objective.

The primary analysis described above will be repeated using data from the Maintenance period only as response. For subjects who did not reach the Maintenance period, their Transition period data will be used to represent their M period data.

This document is confidential.

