### 2.5. Determination of Sample Size

The sample sizes for Zogenix Studies 1501 and 1502 were calculated based on the results of two trials with stiripentol reported in the European Public Assessment Report (EPAR) for stiripentol (EMA, 2007). The stiripentol EPAR summarizes the results from two studies: STICLO France and STICLO Italy. In the stiripentol groups, the standard deviation (SD) of the percentage change in seizure frequency from baseline to month 2 was 42% in the French trial and 26% in the Italian trial. The analogous SDs for placebo groups were 38% and 62%. An SD of 50% was assumed for the primary analysis in Protocols 1501 and 1502 that compares ZX008 0.8 mg/kg/day to placebo on the change from baseline in seizure frequency. Using a two-sided test at the  $\alpha=0.05$  significance level, a sample size of 35 subjects per treatment group affords 90% power to detect a difference in mean change from baseline of 40 percentage points. Similar assumptions and calculations yielded a requirement for an additional 35 subjects in the 0.2 mg/kg/day ZX008 group. The total sample size for each study was therefore set at 105 subjects.

In December 2016 results from a double-blind, placebo-controlled Phase 3 study with Epidiolex® (cannabidiol) to treat seizures in Dravet syndrome were presented at the American Epilepsy Society Meeting (<http://ir.gwpharm.com/events.cfm>). In the Epidiolex study, active drug reduced seizures by 39% compared to a reduction of 13% in the placebo. Review of the data suggested that the standard deviation was relatively large, likely above 50% in both treatment groups. In consideration of this new data, the sample size was re-estimated for the ZX008 studies to assume a SD of 55%, higher than the previous estimate of 50%. Other assumptions in the sample size calculation remained unchanged. A sample size of approximately 120 subjects (40 per arm) affords 90% power to detect a difference in mean change from baseline of 40 percentage points with 55% SD. Considering the variability seen in the STILCO and Epidiolex trials, the sample size for Study 1 and Study 2 is set at 120 subjects, 40 per treatment arm. Note that the change in assumed SD was based entirely on data from external trials. Efficacy data from both Study 1501 and 1502 are still blinded and were not used in re-estimating the required sample size.

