### 2.6. Treatment Assignment & Blinding

Subjects in Study 2 were originally in either Study 1501 or Study 1502. Upon completion of the Baseline Period, subjects who qualify for the study will be randomized (1:1:1) in a double-blind manner to receive 1 of 2 doses of ZX008 (0.2 mg/kg/day, 0.8 mg/kg/day; 30mg/day maximum) or placebo. The randomization was stratified by age (<6 years,  $\geq 6$  years) to ensure balance across treatment arms, with

This document is confidential.

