## Statistical Analysis Plan

Sponsor: Zogenix International Limited; Protocol No.: ZX008 Study 2 (ZX008-1501 and ZX008-1502)

---

day. The ZX008 group will be compared to the placebo group using a rank ANCOVA analogous to that described in Section 8.1 Primary analysis. Specifically, the rank ANCOVA will use the ranks of rescue medication frequency during T+M as the response, and will incorporate treatment group as a factor and the ranks of rescue medication frequency during Baseline as a covariate.

- The number of medications used per episode will be summarized using similar descriptive statistics as above. Rescue medications related to an episode of SE are considered to be all rescue administered on the day of the SE (or seizure lasting > 10 min). If more than one episode of SE or a seizure lasting > 10 min occurred in a single day, the rescue medication for that episode is all rescue administered after the seizure until the start time of the next prolonged seizure.

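### The rank ANCOVA that may decide the primary objective does not say whether age group, the stratification factor, is in the model, and the one rank ANCOVA written out leaves it out

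*SAP*

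**What the plan says.** Randomisation: "The randomization was stratified by age", below 6 years against 6 years and over (Study 2 SAP, 2.6; Study 1 SAP, 3.1).

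Primary analysis (Study 1 SAP, 6.3.1.1; Study 2 SAP, 8.1): the parametric ANCOVA has treatment at three levels, age group and log baseline, with SAS code. The rank version follows in one sentence: "A nonparametric ANCOVA will be used to analyze the data, with ranks of the baseline" frequency as covariate and the ranks of the T+M frequency as response. Neither treatment nor age group is named. If normality is not met, this analysis is used to assess the primary objective. The 0.2 mg/kg/day comparison has the same switch (Study 1 SAP, 6.3.2.1; Study 2 SAP, 8.2.1).

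Rescue medication (Study 1 SAP, 6.3.3.5; Study 2 SAP, 8.2.2): the rank ANCOVA is described as analogous to the one in the primary section. It then specifies that the model "will incorporate treatment group as a factor and the ranks of rescue medication frequency during Baseline as a covariate". Age group is absent.

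Endpoints section of the Study 2 SAP (3.1): the fallback is described only as a nonparametric ANCOVA on rank-transformed seizure frequency.

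**The concern.** The rank ANCOVA can decide Steps 1 and 4 of the gatekeeping sequence (Study 1 SAP, 6.1.2; Study 2 SAP, 6.3), and a failure at Step 1 ends formal testing. Two models fit its one-sentence description, with and without age group, and they give different p-values. That choice should be fixed before unblinding.

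A programmer who looks elsewhere for the model terms finds only the rescue-medication version, which has no age group. Leaving out a stratification factor that predicts outcome keeps its variance in the error term, although the allocation has already balanced it. The standard error is then too large and the test loses power. The fallback would also differ from the parametric model in its covariates as well as its scale.

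**Working it through.** **1. Model terms, side by side**

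| Analysis | Treatment named | Baseline | Age group named |
|---|---|---|---|
| Primary, parametric | yes | log | yes |
| Primary, rank | no | ranked | no |
| Percent change, parametric | yes | untransformed | yes |
| Percent change, rank fallback | no | ranked | no |
| Non-convulsive and total seizures, rank | refers to primary methods | ranked | no |
| Rescue-medication days, rank | yes | ranked | no |

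The plan does name age group elsewhere when it wants it: in the 50% responder logistic model and in the Cochran-Mantel-Haenszel tests for hospitalisation and global impression. No sentence carries it into a rank ANCOVA.

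**2. The plan's own sample size**

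Inputs from the sample-size section (Study 1 SAP, 6.1.10; Study 2 SAP, 2.5): "A sample size of approximately 120 subjects (40 per arm) affords 90% power to detect a difference in mean change from baseline of 40" (in points of percent change); the sample size was "re-estimated for the ZX008 studies to assume a SD of 55" percent; two-sided 0.05.

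n = 2(1.960 + 1.282)² × 55² / 40² = 21.01 × 1.8906 = 39.7, so 40 per arm. Power at 40 is 90.2% by the normal formula and 89.5% by noncentral t. The stated figure reproduces. The earlier figure of 35 per arm at SD 50 also holds: the formula gives 33, and power at 35 is 91.7%.

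**3. Power with and without age, on those inputs**

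Let r be the correlation of age stratum with outcome. The plan gives no r; 0.2, 0.3 and 0.5 are assumptions. Assume strata exactly balanced between arms.

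- SE reported without age: 55 × √(2/40) = 12.30
- True SE under balanced strata: 12.30 × √(1 − r²)
- Critical t (78 df): 1.991, so the rejection limit without age is 1.991 × 12.30 = 24.48
- Power without age ≈ Φ[(40 − 24.48) / true SE]
- Power with age ≈ Φ[40 / true SE − 1.991]

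| r | True SE | Without age | With age | Difference |
|---|---|---|---|---|
| 0 | 12.30 | 89.6% | 89.6% | 0 |
| 0.2 | 12.05 | 90.1% | 90.8% | 0.7 |
| 0.3 | 11.73 | 90.7% | 92.2% | 1.5 |
| 0.5 | 10.65 | 92.7% | 96.1% | 3.4 |

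Noncentral t for the adjusted power gives 92.0% at r = 0.3 and 96.0% at r = 0.5, so differences of 1.3 and 3.3 points. Simulation with exactly balanced strata gives about 0.7, 1.5 and 3.5 points. The correct comparison lets the unadjusted power rise with r. Measuring the gain from a fixed 89.5% would give 1.1, 2.5 and 6.5 points, which is too much.

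**4. What these r values mean**

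With 25% of subjects under 6 (the SAPs say at least 25%), the gap between strata is r × 55 / √(0.25 × 0.75): 25 percentage points at r = 0.2, 38 at 0.3 and 64 at 0.5. The last exceeds the assumed treatment effect of 40.

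**5. The rank ANCOVA itself**

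Simulation of 8,000 trials per setting, N = 120, 1:1:1, 25% under 6. Assumptions not in the documents: block size 6, log-baseline SD 1.0, residual log SD 0.8, baseline slope 0.9, true effect −0.5 log units at the high dose.

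| Age effect (log units) | Type I, without / with age | Power, without / with age |
|---|---|---|
| 0 | 0.052 / 0.052 | 0.741 / 0.740 |
| 0.25 | 0.047 / 0.048 | 0.744 / 0.749 |
| 0.5 | 0.041 / 0.050 | 0.717 / 0.740 |
| 1.0 | 0.027 / 0.049 | 0.649 / 0.736 |

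The two models disagreed on significance in 0.1% to 2.2% of null trials and 0.5% to 8.7% of trials with an effect. An age effect of 1.0 means e^1.0 = 2.7 times the seizure frequency at the same baseline. Losses here can exceed those in step 3 partly because power starts near 74%, where the power curve is steeper.

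**The case against.** A reader might infer that the plan drops age group from the fallback and so ignores the stratified design. The documents do not support that. The rank sentence does not name treatment either, so it cannot be a full list of terms; it says only what is ranked. Section 3.1 of the Study 2 SAP reads naturally as the same ANCOVA on ranks, and no sentence removes age.

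Nor do the other rank analyses explicitly lose age. The percent-change fallback follows a paragraph that names age stratum as a factor and then only replaces values by ranks. The non-convulsive and total-seizure analyses follow the primary methods and inherit whatever those contain. Rescue medication is outside the six-step hierarchy.

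The consequence is also limited. The rank result decides only if normality fails, and both SAPs call the log-scale analysis the main criterion for efficacy. The plan does not use disagreement between the two analyses to diagnose non-normality; the Study 2 SAP plots fitted values and residuals for that. So the difficulty of interpreting a disagreement carries little weight.

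All of this stands, and it limits the point to specification. It does not remove it: the rescue-medication text omits age when read as written, and because it is called analogous to the primary rank ANCOVA, the no-age reading of the decisive fallback is a real one.

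**Conclusion.** The point holds as a specification gap. The plan leaves open whether a potentially decisive model contains the stratification factor, and its one written-out rank model does not contain it.

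If age is omitted, the harm is a conservative test with some lost power, not a false-positive risk. On the plan's percent-change inputs the loss is under 1 point at r = 0.2, about 1 to 1.5 points at r = 0.3 and about 3.5 points at r = 0.5. In the rank simulation it ran from none to about 9 points, the latter under a very strong assumed age effect. All of these rest on assumed age effects, and the percent-change figures are from a t-test, so they only illustrate the rank test. The sample size is unaffected.

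**What to change.** In 6.3.1.1 (Study 1 SAP) and 8.1 (Study 2 SAP), write the rank ANCOVA as treatment (three levels) and age group (<6, ≥6 years) as factors with ranked baseline as covariate, matching the parametric model, and add the code. Bring Section 3.1 of the Study 2 SAP into line. Add age group to the rescue-medication rank ANCOVA in both SAPs. State once that the rank ANCOVAs for the 0.2 mg/kg/day comparison, percent change, non-convulsive seizures and total seizures use the same terms. The cost is wording and one model term, with no new data and no change in sample size.
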